### 1.1.3 Exploratory Objectives

Exploratory Objectives	Endpoints / Variables
CCI [Redacted]	[Redacted]
CCI [Redacted]	[Redacted]
CCI [Redacted]	[Redacted]
CCI [Redacted]	[Redacted]

CCI [REDACTED]

CCI [REDACTED]

a. CCI [REDACTED]

b. CCI [REDACTED]

[figure not shown]
CCI [REDACTED]

## 1.2 Study Design

This is a Phase II, open-label, multi-centre study to determine the safety of a fixed dose of durvalumab 1500 mg monotherapy dose in patients with unresectable Stage III NSCLC who have not progressed following definitive, platinum-based sCRT.

The general study design is summarised in [Figure 1](#).

**Figure 1 Study Design**

a Patients must have received at least 2 cycles of platinum-based chemotherapy before radiation therapy. The interval between administration of the last dose of chemotherapy regimen and start of radiation therapy must be no more than 6 weeks. Consolidation chemotherapy after radiation is not permitted. If the patient's platinum-based chemotherapy contained gemcitabine, no overlap between chemotherapy and radiation therapy is permitted. If the patient's platinum-

based chemotherapy contained cisplatin or carboplatin and etoposide, vinblastine, vinorelbine, a taxane (paclitaxel or docetaxel), or pemetrexed (ie, an agent other than gemcitabine), an overlap of 1 cycle of chemotherapy and radiation therapy is acceptable.

b Treatment initiation within the first 14 days after sCRT therapy is highly encouraged.

AE: adverse event; IP: investigational product; PD: progressive disease; sCRT: sequential chemoradiotherapy; WHO/ECOG PS: World Health Organisation/Eastern Cooperative Oncology Group Performance Status.

Up to 150 patients will be treated with the study drug in Europe and North America in two cohorts: one cohort of between 100 and 120 patients with WHO/ECOG PS=0 or 1, and a second cohort of up to 30 patients with WHO/ECOG PS=2.

Patients must not have progressed following definitive, platinum-based sCRT; radiation therapy must be completed within 42 days prior to first dose administration of durvalumab. The last dose of radiation therapy is defined as the day of the last radiation treatment session.

Patients must have histologically- or cytologically-documented NSCLC and locally-advanced, unresectable Stage III disease (according to the International Association for the Study of Lung Cancer [IASLC] Staging Manual Version 8 [IASLC 2016])

### 1.2.1 Study Treatment

Patients will receive 1500 mg durvalumab administered via intravenous (IV) infusion, starting on Week 1 after confirmation of eligibility, every four weeks (q4w) for a maximum of 24 months from Cycle 1 Day 1. Study drug should be discontinued prior to 24 months if there is progressive disease according to RECIST 1.1 criteria (PD; unless the investigator considers the patient continues to receive benefit from the durvalumab), initiation of alternative cancer therapy, unacceptable toxicity, withdrawal of consent, or another discontinuation criterion is met.

Patients may delay dosing due to TRAEs which are either immune-mediated AEs (imAEs) or non-imAEs, or for reasons other than TRAEs.

- In case of a TRAE (imAEs or non-imAEs), dosing may be delayed per the Dosing Modification and Toxicity Management Guidelines (see annex to the protocol).
- If dosing must be delayed for reasons other than TRAEs, dosing will resume as soon as feasible.
- The duration of delays will be accounted for, as a non-exposure duration, when deriving actual duration of exposure to study treatment (See Section [3.2.8](#))

The schedule of assessments including safety, tolerability, efficacy using RECIST version 1.1 and patient reported outcomes (PROs) based on questionnaires are detailed in the study assessment schedule in [Appendix A](#).

If the dosing is delayed, the laboratory and physical assessments scheduled for that treatment cycle will also be delayed accordingly. The tumour efficacy and PRO assessments dates are not affected by dose delays and remain as originally scheduled, as they are based on the date of first administration of durvalumab (not the date of the study therapy per cycle).

All other scheduled assessments must be performed relative to the start of the dosing cycle such that all procedures required for dosing (eg, collection of laboratory samples) should be

performed within 3 calendar days prior to dosing.

The assessment of electrocardiogram (ECG), urinalysis and coagulation are scheduled to be performed as clinically indicated.

If the recording of vital signs, ECG and blood draws for laboratory tests are scheduled at a visit, they will always be performed in the order: ECG, vital signs and blood draws. In case only two measurements are scheduled, this order will be maintained.

### 1.2.2 Tumour Response Assessments

Tumour assessments using computed tomography (CT)/magnetic resonance imaging (MRI) will be performed at the times specified in the schedule of assessment ([Appendix A](#)). RECIST 1.1 measurements as assessed by the Investigator will be used to derive the secondary variables of PFS, ORR, and DoR. The categorization of objective tumour response assessment into complete response (CR), partial response (PR), stable disease (SD), progressive disease (PD) or not evaluable (NE) will be based on RECIST 1.1.

### 1.2.3 Overall Survival Assessments

Patients will be followed for survival status every 12 weeks (q12w) following treatment discontinuation, until death, withdrawal of consent or the end of the study. These contacts may be conducted by phone and the survival data collected will be reported in the clinical database for the final study analysis.

## 1.3 Number of Subjects

This is a safety study and no formal sample size calculation has been performed. Up to 150 patients will be treated with the study drug in 2 cohorts: Between 100 and 120 patients in the WHO/ECOG PS 0 to 1 Cohort and up to 30 patients in the WHO/ECOG PS 2 Cohort.

The primary analysis will be performed when the last patient dosed had the opportunity to receive durvalumab (MEDI4736) for six months. If, as observed in the PACIFIC study, Grade 3 or 4 TRAEs were to occur in 8.3% of the 120 patients in this study (ie, 10 patients), the 95% Clopper-Pearson confidence interval (CI) for this incidence would be 4.1% to 14.8% (approximately  $\pm 5.35\%$ ). Furthermore, if Grade 3 or 4 TRAEs were to occur in 12% of 100 patients in the WHO/ECOG PS 0 to 1 cohort (ie, 12 patients), the 95% CI would be 6.4% to 20.0% (approximately  $\pm 6.8\%$ ), if they occurred in 13.3% of 30 patients in the WHO/ECOG PS 2 cohort (ie, in 4 patients), the 95% CI would be 3.8% to 30.7% (approximately  $\pm 13.5\%$ ).

A further illustration of the estimated incidence rate and Clopper-Pearson 95% CI for varying numbers of subjects observed with Grade 3 or 4 TRAEs for all patients and within each WHO/ECOG PS 2 Cohort is provided in [Table 1](#).

**Table 1 Precision of estimation of varying incidence rates of Grade 3 or 4 TRAEs**

All Patients (n=120)	Number of subjects with a Grade 3 or 4 TRAEs	8	10	14	18	24
	Estimated Incidence (%)	6.7	8.3	11.7	15.0	20.0

	95% CI (%)	2.9, 12.7	4.1, 14.8	6.5, 18.8	9.1, 22.7	13.3, 28.3
WHO/ECOG PS 0 to 1 Cohort (n=100)	Number of subjects with a Grade 3 or 4 TRAEs	7	8	12	15	20
	Estimated Incidence (%)	7.0	8.0	12.0	15.0	20.0
	95% CI (%)	2.9, 13.9	3.5, 15.1	6.4, 20.0	8.7, 23.5	12.7, 29.2
WHO/ECOG PS 2 Cohort (n=30)	Number of subjects with a Grade 3 or 4 TRAEs	2	3	4	5	7
	Estimated Incidence (%)	6.7	10.0	13.3	16.7	23.3
	95% CI (%)	0.8, 22.1	2.1, 26.5	3.8, 30.7	5.6, 34.7	9.9, 42.3

Note: Clopper-Pearson confidence intervals are shown.

AE: Adverse event; CI: Confidence interval; n: Number of patients; TRAE: Treatment-related adverse event;  
 WHO/ECOG PS: World Health Organisation/Eastern Cooperative Oncology Group Performance Status.

## 2. ANALYSIS SETS

### 2.1 Definition of Analysis Sets

With the exception of some summaries of patient disposition and particular individual patient data listings, which will be produced for all patients who provided informed consent and who were enrolled in the study, the Safety Analysis Set (SAF) will be used for listings, summaries, and analyses in the study.

#### 2.1.1 Safety Analysis Set (SAF)

The SAF will consist of all patients who received at least one dose (partial or in full) of durvalumab.

In this study, Full Analysis Set (FAS) will consist of all patients who received at least one dose (partial or in full) of durvalumab. Therefore, the SAF and FAS would be equivalent in this study and for the purpose of results presentation all endpoints will be analysed using SAF.

## 2.2 Protocol Deviations

### 2.2.1 Important Protocol Deviations

According to ICH E3 guidelines version dated 1995 ([ICH 1995](#)),

“Protocol deviations consist of any change, divergence or departure from the study design or procedures defined in the protocol. Important protocol deviations (IPDs) are a subset of protocol deviations that may significantly affect the completeness, accuracy, and/or reliability of the study data or that may significantly affect a patient’s rights, safety or well-being.”

For this study, the following 4 general categories will be considered IPDs and will be summarized in the CSR:

- Deviation 1: Patients who received treatment and who deviated from the following key entry criteria in CSP:
  - Inclusion Criterion 5: Histologically- or cytologically-documented NSCLC with locally-advanced, unresectable Stage III disease (according to the IASLC 2016]). Positron emission tomography (PET)/CT, MRI of the brain, and endobronchial ultrasound with biopsy are highly encouraged at diagnosis.
  - Inclusion Criterion 6: Receipt of sCRT which must have been completed within 42 days prior to first dose administration of durvalumab in the study.
    - (a) The platinum-based chemotherapy regimen must contain cisplatin or carboplatin and 1 of the following agents: etoposide, vinblastine, vinorelbine, a taxane (paclitaxel or docetaxel), or pemetrexed, according to the local SoC regimens. Platinum-based chemotherapy containing cisplatin or carboplatin and gemcitabine is permitted under certain conditions – refer to bullet point 6(b).
    - (b) Patients must have received at least 2 cycles of platinum-based chemotherapy before radiation therapy. The interval between administration of the last dose of chemotherapy regimen and start of radiation therapy must be no more than 6 weeks. Consolidation chemotherapy after radiation is not permitted.
      - (i) If the patient’s platinum-based chemotherapy contained gemcitabine, no overlap between chemotherapy and radiation therapy is permitted.
      - (ii) If the patient’s platinum-based chemotherapy contained any of the agents listed in 6(a) other than gemcitabine, an overlap of 1 cycle of chemotherapy and radiation therapy is acceptable.
    - (c) Patients must have received a total dose of radiation of 60 Gray (Gy)  $\pm$ 10% (54 Gy to 66 Gy). Sites are encouraged to adhere to mean organ radiation dosing as follows:
      - (i) Mean lung dose <20 Gy and/or V20 <35%;
      - (ii) Mean oesophagus <34 Gy;
      - (iii) Heart V45 <35% or V30 <30%.
  - Note: Sites should be aware of the recent Radiotherapy Oncology Group (RTOG) version 0617 (RTOG 0617) Study data demonstrating that doses higher than 60 Gy may be associated with greater toxicity and worse efficacy.
  - (d) Patients with WHO/ECOG PS 2 or chronic lung disease (pulmonary emphysema or chronic obstructive pulmonary disease) must have received a V20 <25%.
- Inclusion Criterion 7: Patients must not have progressed following platinum-based sCRT, as per Investigator-assessed RECIST 1.1 criteria. In order to assess disease progression, the baseline imaging (CT/MRI) used for Screening purposes should be compared against the most recently performed scan that allows physician assessment as per RECIST 1.1 criteria (i.e. fulfils the RECIST 1.1 defined imaging acquisition parameters). If an intermediate scan taken between chemotherapy and radiotherapy is available and that scan is suitable for physician assessment as per RECIST 1.1

criteria, then this scan should be used.

(a) Patients with measurable disease and/or non-measurable and/or no evidence of disease (NED) assessed at baseline by CT/MRI will be entered in this study.

(b) Prior irradiated lesions may be considered measurable and selected as TLs provided they fulfil the other criteria for measurability.

- Inclusion Criterion 9: WHO/ECOG PS  $\leq 2$ .
- Exclusion Criterion 1: Patients with locally-advanced NSCLC whose disease has progressed following platinum-based sCRT.
- Exclusion Criterion 2: Patients who have disease considered for surgical treatment as part of their care plan, such as Pancoast or superior sulcus tumours.
- Exclusion Criterion 3: Mixed small-cell lung cancer and NSCLC histology.
- Exclusion Criterion 6: Uncontrolled intercurrent illness, including but not limited to, ongoing or active infection, symptomatic congestive heart failure, uncontrolled hypertension, unstable angina pectoris, cardiac arrhythmia, Interstitial lung disease (ILD), serious chronic Gastrointestinal (GI) conditions associated with diarrhoea, or psychiatric illness/social situations that would limit compliance with study requirement, substantially increase risk of incurring AEs, or compromise the ability of the patient to give written informed consent.
- Exclusion Criterion 13: Patients who have received cCRT for locally-advanced NSCLC, or who received sCRT with at least 2 concomitant CRT cycles. Prior surgical resection (ie, Stage I or II) is permitted.  
  
Note: Patients whose platinum-based chemotherapy contained gemcitabine and who received sCRT with at least 1 concomitant CRT cycle are excluded from this study.
- Exclusion Criterion 16: Prior exposure to immune-mediated therapy, including but not limited to, other anti-CTLA-4, anti-PD-1, anti-PD-L1, and anti-PD-L2 antibodies, excluding therapeutic anticancer vaccines.
- Deviation 2: The patient met discontinuation criteria but did not discontinue durvalumab (eg, patient withdrew consent, patient became pregnant).
- Deviation 3: The patient received a prohibited concomitant medication or procedure as detailed in Section 6.4 of the CSP or any other concomitant medication or procedure which, upon physician review of all medications and procedures prior to database lock (DBL), is considered to have a potential effect on study outcomes.
- Deviation 4: Missed visits, assessments, or treatments that, in the opinion of the principal investigator,
  - were due to the 2020 COVID-19 global pandemic and
  - there was a significant effect on either completeness, accuracy, and/or reliability of the patient's data, or the patient's rights, safety or well-being.

### **2.2.2 Monitoring of Important Protocol Deviations**

Programmable PDs will be detected from the data recorded in the clinical database and will be reviewed at regular PD review meetings. At this meeting, the programmatically-derived PDs will be checked to ensure that they have been correctly classified as major or minor PDs.

On an ongoing basis throughout the study, monitoring notes or summaries will also be reviewed to determine any important post-entry deviations that are not identifiable via programming.

If the number of deviations which are considered to have the potential to impact the primary analysis is considered important, sensitivity analyses may be performed on subgroups. This will be decided during the data review meeting and before the database lock.

The final classification of IPDs will be made prior to database lock or data cut-off (DCO) for final analysis. Any other deviations from monitoring notes or reports will be reported in an appendix to the CSR.

## **3. ANALYSIS VARIABLES**

### **3.1 Derivation of RECIST Visit Responses**

For all patients, the RECIST tumour response data will be used to determine each patient's visit response according to RECIST version 1.1. It will also be used to determine, if and when a patient's disease has progressed in accordance with RECIST and their best objective response to study treatment.

The baseline radiological tumour assessment is part of the screening procedure and should be performed within 42 days after the end of sCRT, no more than 28 days before the start of durvalumab treatment, and ideally as close as possible to the start of study treatment. Tumour assessments will begin at 8 weeks  $\pm$  1 week after durvalumab initiation and continue every 8 weeks  $\pm$  1 week through 52 weeks (relative to the date of durvalumab initiation), and then every 12 weeks  $\pm$  1 week thereafter until disease progression. An additional follow-up scan will be performed if clinically feasible.

If an unscheduled assessment is performed, and the patient's disease has not progressed, every attempt should be made to perform the subsequent assessments at patients' scheduled visits. This schedule is to be followed to minimise any unintentional bias caused by some patients being assessed at a different frequency than other patients.

Additional scans can be completed per standard practice post-disease progression.

From the investigator's review of the imaging scans, the RECIST tumour response data will be used to determine each patient's visit response according to RECIST version 1.1. At each visit, patients will be programmatically assigned a RECIST 1.1 visit response of CR, PR, SD or PD, using the information from target lesions (TLs), non-target lesions (NTLs) and new lesions and depending on the status of their disease compared with baseline and previous assessments. If a patient has had a tumour assessment which cannot be evaluated, then the patient will be assigned a visit response of not evaluable (NE) (unless there is evidence of progression in which case the

response will be assigned as PD).

RECIST outcomes (ie, PFS and ORR etc.) will be calculated programmatically from site investigator data from overall visit responses.

### **3.1.1 Site Investigator Assessments Using RECIST 1.1**

#### **3.1.1.1 Target Lesions**

Measurable disease is defined as having at least one measurable lesion, not previously irradiated, which is  $\geq 10$  mm in the longest diameter (LD), (except lymph nodes which must have short axis  $\geq 15$  mm) with CT or MRI and which is suitable for accurate repeated measurements.

A maximum of five measurable lesions (with a maximum of two lesions per organ), representative of all lesions involved and suitable for accurate repeated measurement, should be identified as target lesions (TLs) at baseline. It may be the case that, on occasion, the largest lesion does not lend itself to reproducible measurement. In which circumstance the next largest lesion, which can be measured reproducibly, should be selected. If more than one baseline scan is recorded, then measurements from the one that is closest and prior to initiation of durvalumab will be used to define the baseline sum of TLs.

All other measurable lesions not recorded as TL, and all non-measurable lesions (or sites of disease) should be identified as non-target lesions (NTLs) at baseline. Measurements are not required for these lesions, but their status should be followed at subsequent visits.

For patients who do not have measurable disease at entry (ie, no TLs) but have non-measurable disease, evaluation of overall visit responses will be based on the overall NTL assessment and the absence/presence of new lesions (see Section 3.1.1.3 for further details). If a patient does not have measurable disease at baseline, then the TL visit response will be not applicable (NA).

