 - (iii) Heart V45 <35% or V30 <30%.Note: Sites should be aware of the recent RTOG 0617 Study data demonstrating that doses higher than 60 Gy may be associated with greater toxicity and worse efficacy.
 - (d) Patients with WHO/ECOG PS 2 or chronic lung disease (pulmonary emphysema or chronic obstructive pulmonary disease) must have received a V20 <25%.
- 7 Patients must not have progressed following platinum-based sCRT, as per Investigator-assessed RECIST 1.1 criteria. In order to assess disease progression, the baseline imaging (CT/MRI) used for Screening purposes should be compared against the most recently performed scan that allows physician assessment as per RECIST 1.1 criteria (i.e. fulfils the RECIST 1.1 defined imaging acquisition parameters). If an intermediate scan taken between chemotherapy and radiotherapy is available and that scan is suitable for physician assessment as per RECIST 1.1 criteria, then this scan should be used.
 - (a) Patients with measurable disease and/or non-measurable and/or no evidence of disease (NED) assessed at baseline by CT/MRI will be entered in this study.
 - (b) Prior irradiated lesions may be considered measurable and selected as TLs provided they fulfil the other criteria for measurability.
- 8 Must have a life expectancy of at least 12 weeks at enrolment.
- 9 WHO/ECOG PS \leq 2.
- 10 Adequate organ and marrow function at enrolment as defined below. These parameters should be achieved without augmentation by growth factors, transfusions, or infusions within 14 days of screening unless required for SoC:
 - (a) Haemoglobin \geq 9.0 g/dL;
 - (b) Absolute neutrophil count $>1.0 \times 10^9/L$;

- (c) Platelet count $>75 \times 10^9/L$;
- (d) Serum bilirubin $\leq 1.5 \times$ upper limit of normal (ULN). This will not apply to patients with confirmed Gilbert's syndrome, who will be allowed in consultation with their physician.
- (e) Alanine aminotransferase (ALT) and aspartate aminotransferase (AST) $\leq 2.5 \times$ ULN.
- (f) Measured creatinine clearance >40 mL/min or calculated creatinine clearance >40 mL/min as determined by Cockcroft-Gault (using actual body weight) ([Cockcroft and Gault 1976](#)).

Males:

$$\text{Creatinine clearance (mL/min)} = \frac{\text{Weight (kg)} \times (140 - \text{Age})}{72 \times \text{serum creatinine (mg/dL)}}$$

Females:

$$\text{Creatinine clearance (mL/min)} = \frac{\text{Weight (kg)} \times (140 - \text{Age})}{72 \times \text{serum creatinine (mg/dL)}} \times 0.85$$

Weight

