#### 1.1.2 Secondary Objectives

Secondary Efficacy Objectives	Endpoints / Variables
To assess the efficacy of durvalumab treatment in terms of progression-free survival (PFS) and overall survival (OS)	Median PFS according to Response Evaluation Criteria in Solid Tumours version 1.1 (RECIST 1.1) as assessed by the Investigator  PFS12 and PFS24 according to RECIST 1.1 as assessed by the Investigator  Median OS, OS12, OS24, and OS36
To further assess the efficacy of durvalumab treatment in terms of objective response rate (ORR) and duration of response (DoR)	ORR according to RECIST 1.1 as assessed by the Investigator  DoR according to RECIST 1.1 as assessed by the Investigator
To assess the efficacy of durvalumab treatment in terms of lung cancer mortality	Lung cancer mortality

Secondary Safety Objectives	Endpoints / Variables
To further assess the safety and tolerability profile of durvalumab treatment, including all adverse events (AEs)	AEs, serious adverse events (SAEs), adverse events of special interest (AESIs), immune-mediated adverse events (imAEs), physical examinations, vital signs including blood pressure (BP) and pulse rate, respiratory rate, temperature, ECGs, and laboratory findings including clinical chemistry, haematology and urinalysis

Note: Analysis of ORR and DoR will be based upon Investigator assessment according to RECIST 1.1. Prior irradiated lesions may be considered measurable and selected as target lesions providing they fulfil the other criteria for measurability.

Note: An AESI is an AE of scientific and medical interest specific to understanding of the durvalumab. AESIs for durvalumab include, but are not limited to, events with a potential inflammatory or immune-mediated mechanism and which may require more frequent monitoring and/or interventions such as steroids, immunosuppressants and/or hormone replacement therapy.

Note: An imAE is defined as an AESI that is associated with drug exposure and is consistent with an immune-mediated mechanism of action and where there is no clear alternate etiology.

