### **Irradiated Lesions/Lesion Intervention**

A previously irradiated lesion may be selected as a TL, provided that it fulfils the criteria for reproducible measurability and is the only lesion available.

Any TL (including lymph nodes), which has had intervention in addition to study treatment during the study (eg, irradiation / palliative surgery / embolization), should be handled in the

following way and once a lesion has had intervention then it should be treated as having intervention for the remainder of the study noting that an intervention will most likely shrink the size of tumours:

- Step 1: the diameters of the TLs (including the lesions that have had intervention) will be summed and the calculation will be performed in the usual manner. If the visit response is PD this will remain as a valid response category.
- Step 2: If there was no evidence of progression after step 1, treat the lesion diameter (for those lesions with intervention) as missing and if  $\leq 1/3$  of the TLs have missing measurements then scale up as described in the 'Scaling' section below. If the scaling results in a visit response of PD then the patient would be assigned a TL response of PD.
- Step 3: If, after both steps, PD has not been assigned, then, if appropriate (ie, if  $\leq 1/3$  of the TLs have missing measurements), the scaled sum of diameters calculated in step 2 should be used, and PR or SD then assigned as the visit response. Patients with intervention are evaluable for CR as long as all non-intervened lesions are 0 (or <10mm for lymph nodes) and the lesions that have been subject to intervention have a value of 0 (or <10mm for lymph nodes) recorded. If scaling up is not appropriate due to too few non-missing measurements, then the visit response will be set as NE.

At subsequent visits the above steps will be repeated to determine the TL and overall visit response. When calculating the previous minimum, lesions with intervention should be treated as missing and scaled up (as per step 2 above).

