### 3.3.3 Objective Response Rate

The ORR is defined for the SAF as follows:

- The ORR is the proportion (%) of patients with an overall response of CR or PR (confirmed by a follow-up scan at least 4 weeks after showing CR or PR).

A confirmed response of CR/PR means that a response of CR/PR is recorded at one visit and confirmed by repeat imaging, preferably at the next regularly scheduled imaging visit, and not less than four weeks after the visit when the response was first observed, with no evidence of progression between the initial and CR/PR confirmation visit. Both visits contributing to the confirmed response must be prior to any subsequent anti-cancer therapy for the patient to be considered as a responder.

Data obtained up until progression, or the last evaluable assessment in the absence of progression, will be included in the assessment of the ORR. Responses that occur after the start of subsequent anti-cancer therapy must be excluded from the derivation of ORR (ie, only responses that occur prior to receiving subsequent therapy will be included in the numerator).

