### 3.3.4 Best Objective Response

Best objective response (BoR) is the best response a patient has had after Day 1 up until progression, or the last evaluable assessment in the absence of progression. Responses that occur after the start of subsequent anti-cancer therapy must be excluded from the derivation. Categorization of BoR will be based on RECIST using the following response categories: CR, PR, SD, PD and NE.

CR or PR must be confirmed. For determination of a best response of SD, the earliest of the dates contributing towards a particular overall visit assessment will be used. SD should be recorded at least 8 weeks minus 1 week, ie, at least 49 days (to allow for an early assessment within the assessment window), after durvalumab initiation. For CR/PR, the initial overall visit assessment that showed a response will use the latest of the dates contributing towards a particular overall visit assessment.

For patients whose progression event is death, BoR will be calculated based upon all evaluable

RECIST assessments prior to death.

For patients who die with no evaluable RECIST assessments, if the death occurs  $\leq 9$  weeks (ie, 8 weeks + 1 week to allow for a late assessment within the assessment window) after durvalumab initiation, then BoR will be assigned to the progression (PD) category. For patients who die with no evaluable RECIST assessments, if the death occurs  $> 9$  weeks after Day 1 then BoR will be assigned to the NE category.

A patient will be classified as a responder if the RECIST criteria for a CR or PR are satisfied at any time following Day 1, prior to RECIST progression and prior to starting any subsequent cancer therapy.

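### SAP 3.1.1.1 contradicts the rest of the plan on irradiated target lesions, and the all-treated ORR includes patients who cannot respond, with no supportive analysis and no NED category for best response

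*SAP*

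**What the plan says.** **Irradiated lesions.** The documents give three rules.

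- SAP 3.1.1.1, opening: "Measurable disease is defined as having at least one measurable lesion, not previously irradiated". The same passage of text ends by making the target-lesion (TL) response not applicable (NA) for a patient without measurable disease at baseline.
- SAP 1.1.2, note: "Prior irradiated lesions may be considered measurable and selected as target lesions providing they fulfil the other criteria for measurability". Protocol inclusion criterion 7(b) agrees: "Prior irradiated lesions may be considered measurable and selected as TLs provided they fulfil the other criteria for measurability".
- SAP 3.1.1.1, Irradiated Lesions/Lesion Intervention: "A previously irradiated lesion may be selected as a TL", but only "provided that it fulfils the criteria for reproducible measurability and is the only lesion available". Protocol Appendix F carries the same condition. Its own definition of a measurable lesion rests on size and repeatability and does not mention earlier irradiation.

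Inclusion criterion 6(c) requires 54 to 66 Gy in every patient.

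**Denominator and best response.** Inclusion criterion 7(a) says: "Patients with measurable disease and/or non-measurable and/or no evidence of disease (NED) assessed at baseline by CT/MRI will be entered in this study". SAP 3.3.3 says: "The ORR is the proportion (%) of patients with an overall response of CR or PR". The response must be confirmed, and ORR is defined on the safety analysis set (SAF), which SAP 2.1.1 makes everyone given any durvalumab. SAP Table 4 includes NED as an overall visit response, but SAP 3.3.4 says: "Categorization of BoR will be based on RECIST using the following response categories: CR, PR, SD, PD and NE". SAP 4.4.3 plans no ORR restricted by baseline disease status.

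**The concern.** SAP 3.1 has visit responses and RECIST outcomes derived by program from the investigator's data, so the programmer has to follow one of these rules. With prior radiotherapy universal, the choice can affect a large part of the population. If an irradiated lesion does not count as a TL, the patient is assessed on non-target lesions (NTLs) only and PR is no longer attainable. The progression rule changes too: a TL progresses on a 20% and 5 mm increase (SAP Table 2), an NTL only on unequivocal worsening (SAP Table 3).

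The denominator issue is separate. The all-treated ORR combines how often disease responds with how many patients entered with disease that could be scored as responding. Without a companion analysis a reader cannot separate the two, overall or within each PS cohort. The BoR table also gives no instruction for a patient whose visits are all NED.

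**Working it through.** **Step 1: what can be reproduced.** The documents state no expected ORR, no ORR precision, and no share of patients with NED or without a TL. The exact (Clopper-Pearson) method the SAP uses can be checked against SAP Table 1: 10/120 gives 4.1 to 14.8%, 12/100 gives 6.4 to 20.0%, and 4/30 gives 3.8 to 30.7%, as printed. All 15 intervals agree within 0.1 point.

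**Step 2: the three rules applied to one patient.** Take an irradiated primary and an irradiated node, both large enough to measure, and no other lesion.

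| Rule | Target lesions | PR possible? |
|---|---|---|
| SAP 3.1.1.1, opening, read literally | None; TL response NA | No |
| SAP 1.1.2 and criterion 7(b) | Both may be chosen | Yes |
| SAP 3.1.1.1 later paragraph and Appendix F | Unclear: neither is the sole lesion | Depends on reading |

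**Step 3: routes to response in SAP Table 4.**

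- TL present: CR or PR available.
- No TL, NTLs present: CR, SD, PD or NE; no PR.
- Neither TL nor NTL: NED, or PD if a new lesion appears; never CR or PR.

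**Step 4: dilution of the all-treated ORR.** Let r be the ORR in patients with a TL, f the share without one (including NED), and c the CR rate in that share (c = 0 for NED). Then

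ORR on the SAF = r(1 − f) + c·f.

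Assumptions: r = 28.4%, the durvalumab response rate quoted for PACIFIC in Protocol Section 2, used only as an illustration; f is not in the documents, so a range is shown. With c = 0:

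- f = 5%: 28.4 × 0.95 = 27.0%
- f = 10%: 28.4 × 0.90 = 25.6%
- f = 20%: 28.4 × 0.80 = 22.7%
- f = 30%: 28.4 × 0.70 = 19.9%

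CRs in NTL-only patients soften this. At f = 20% and c = 5%: 22.7 + 5 × 0.20 = 23.7%. At f = 0 there is no effect.

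In counts, with 150 treated and f = 20% (120 with a TL, 34 responders): 34/150 = 22.7% (95% CI 16.2 to 30.2) on the SAF, and 34/120 = 28.3% (20.5 to 37.3) among patients with a TL. Interval widths are 14.0 and 16.8 points.

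**Step 5: the literal irradiation reading, for scale only.** If a share m of patients kept a non-irradiated TL, ORR = r·m + c(1 − m). At m = 50%: 28.4 × 0.5 = 14.2% with c = 0, or 14.2 + 5 × 0.5 = 16.7% with c = 5%. The documents give no m.

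**The case against.** The irradiation clause may never take effect. SAP 3.1.1.1 itself glosses absence of measurable disease as having no TLs. SAP Table 2 ties the NA response to whether any TL was recorded at baseline, not to irradiation history. The later paragraph of 3.1.1.1 admits irradiated TLs. Investigators choose lesions under the protocol, whose definition of measurability has no irradiation exclusion, and no SAP step discards a TL once recorded. This stands: a recorded irradiated TL would probably be kept. A reader might infer that PR is closed to nearly all patients and that ORR is structurally deflated by this clause. That requires one phrase to override the rest of the plan. It also requires every lesion to have been irradiated, which a total dose of 54 to 66 Gy per patient does not show.

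The all-treated denominator is explicit and consistent (Protocol 9.3, SAP 2.1.1 and 3.3.3) and defensible in a single-arm study with no hypothesis test. This stands too. Restricting the main analysis to patients with a TL would depart from the protocol and drop genuine CRs in NTL-only patients.

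Two further inferences go beyond the text. The first is that NED patients will be counted as NE and inflate that category. SAP 3.3.4 does not map NED to anything, and the default in SAP 4.1.1 of using non-missing data as the denominator does not settle it, so the gap is an unspecified mapping. The second is that the PS cohorts cannot be compared. The plan reports them separately and descriptively, and no imbalance in baseline disease is shown. SAP 3.5.1 collects evidence of disease at entry, which helps but does not replace an ORR by that status.

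**Conclusion.** The point holds in two parts.

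First, the SAP contradicts itself and the protocol on whether an irradiated lesion can be measurable, and both documents are inconsistent on whether it must be the only lesion. The literal reading of the opening of 3.1.1.1 would remove irradiated TLs and the route to PR, but SAP Table 2 and the later paragraph point the other way. This is a wording conflict to settle before programming is final, not a demonstrated loss of response.

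Second, the all-treated ORR is lowered relative to ORR in patients with a TL if patients with NED are treated, and also by NTL-only patients to the extent that their CR rate is below that ORR. The size cannot be derived from the documents. The illustrative drop from 28.4% to 25.6% (f = 10%) or 22.7% (f = 20%) assumes the PACIFIC rate and no responses among patients without a TL. Best response has no stated place for NED.

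ORR is secondary and untested, and the primary safety analysis is unaffected. This is a should-fix.

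**What to change.** 1. Delete the irradiation exclusion from the definition of measurable disease in SAP 3.1.1.1.
2. Decide whether the only-lesion condition applies, and make SAP 1.1.2, SAP 3.1.1.1, inclusion criterion 7(b) and Protocol Appendix F say the same thing, so that one target-lesion rule governs.
3. Keep the all-treated ORR as the main analysis. Add supportive ORR and BoR, overall and by PS cohort, in (a) patients with at least one TL at baseline and (b) patients with any disease at baseline. Set (b) retains CRs in NTL-only patients.
4. Add NED to the BoR categories in SAP 3.3.4 and 4.4.3.
5. Leave DoR unchanged: it is defined only in responders, so the denominator does not affect it.

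The cost is SAP wording, a clarification on the protocol side for item 2, baseline-disease flags and one extra table. The supportive intervals are somewhat wider because their denominators are smaller (16.8 against 14.0 points in the example above).
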